### 4.2 Exclusion Criteria

Patients with the following will be ineligible for registration onto this study:

1. History of treatment with a tyrosine kinase inhibitor (eg, imatinib) or other moderate-to-significant CYP4A inhibitor within 2 weeks of enrollment.
2. Renal insufficiency as follows: creatinine  $> 2.5$  mg/dL or CrCl  $< 30$  ml/min.
3. Hepatic insufficiency as follows: serum bilirubin  $> 3$  mg/dL or grade 3 or greater transaminitis at baseline (even if deemed due to GVHD) or cirrhosis (any Childs Pugh class).
4. History of cardiac dysrhythmias or known cardiovascular disease without formal Cardiology clearance.
5. History of cerebro-vascular accident or intracranial hemorrhage within 6 months prior to enrollment.
6. History of non-intracranial hemorrhage and/or coagulopathy without formal Coagulation clearance.
7. Uncontrolled infections not responsive to antibiotics, anti-viral medicines, or anti-fungal medicines; or infection requiring systemic treatment that was completed  $\leq 14$  days before enrollment.
8. History of other hematologic malignancy.
9. History of human immunodeficiency virus (HIV).
10. History of active hepatitis B virus (HBV) or hepatitis C virus (HCV) without formal Infectious Disease clearance.
11. Patients incapable of complying with routine follow up schedule or unable to be compliant with study therapy.
12. Active or within 3 months use of prohibited medications or substances (e.g., illicit drugs).

### 4.3 Subject Recruitment and Screening

- Patients will be recruited from the Norris Cotton Cancer Center. Subjects will have demonstrated active cGVHD and either primary refractoriness to a trial of steroids (Methyl-prednisolone or prednisone at a dose range of 0.5-2 mg/kg/day) or intolerance to a steroid taper *prior to* being enrolled in this study and beginning ibrutinib and rituximab therapy.

The study will be introduced to patients during clinical appointments if they meet eligibility criteria. Informed consent, including purpose of the study, risks and benefits of participation, and rights of participants, will be discussed either at that time or separately by available study staff in an individual session.

In order to confirm and assess the extent of GVHD and meet inclusion criteria, this study may require evaluation of participants by utilizing various diagnostic measures (within one week of enrollment):

Medical history

Physical examination, including height and weight  
Blood studies (baseline CBC/diff, CMP, PT/PTT)  
Urinalysis, culture, urine for CrCl, as indicated  
Additional studies, as clinically indicated

Studies pertinent to the organ system under consideration for the diagnosis of chronic GVHD

-biopsy proven or strong clinical suspicion of a chronic GVHD diagnosis will be required

New pregnancy test

New comprehensive infectious work-up with negative findings in the appropriate clinical setting (eg, Pulmonary cGVHD) will be required

The decision to obtain tests and procedures noted above will depend on the individual clinical scenario. The guidelines for standard cGVHD intervention will be followed.

## **4.4 Early Withdrawal of Subjects**

### **4.4.1 When and How to Withdraw Subjects**

A subject may choose to not be in this study at any time. Leaving the study will not affect regular medical care in any way. Participants will be asked to contact study staff if they are thinking about leaving the study. In addition, a follow-up visit will be utilized to ensure the safety of any participant who chooses to discontinue enrollment on this study. Any subject withdrawing from the study prematurely due to toxicity will be evaluable for toxicity and will not be replaced. Subjects withdrawing from the study for reasons other than toxicity (eg, due to relapse of malignancy) will be replaced. All subjects remaining on the study for at least 6 weeks will be evaluable for efficacy.

Any protocol physician may stop the study at any time. In addition, participants may be asked to leave the study. Possible reasons to terminate participation may include:

1. Serious side effect ( $\geq$  grade 4 adverse event)
2. Inability to tolerate dose of medication.
3. No longer meeting criteria for this study.
4. Development of new conditions needing other treatments.
5. Emergence of new therapy or studies.
6. Progression of disease.
7. Personal choice of the subject to stop study participation.

### **4.4.2 Data Collection and Follow-up for Withdrawn Subjects**

If a subject withdraws consent to participate in the study, attempts will be made to obtain permission to record data (including survival data) up to the protocol-described end of the subject's follow-up period. In such an instance, the patient will be contacted by phone.

## **5 Study Drug**

### **5.1 Treatment Regimen**

#### **Rituximab**

\*375 mg/m^2 IV infusion weekly for 4 (may repeat 8 weeks after initial therapy, if suboptimal response)

#### **Ibrutinib**

\*420 mg (140 mg capsule x3) by mouth daily

\* May be given beyond 3-6 months (for maintenance).

### 5.1.1 Details of the Treatment Regimen

**Initial cohort (first 5 patients accrued) will be treated as follows:**

Ibrutinib 140 mg po once daily with

Rituximab 375 mg/m^2 IV weekly x4 (with pre-medications and infusion procedure as per standard protocol)

Rituximab Pre-medications: Acetaminophen 650 mg po; Diphenhydramine 25 mg po/IV; Dexamethasone 20 mg IV

If no adverse events  $\geq$  nonhematologic grade 3 or  $\geq$  hematologic grade 4 are noted after 1 week at 140 mg daily, the Ibrutinib dose schedule will be increased to 280 mg daily

If no adverse events  $\geq$  nonhematologic grade 3 or  $\geq$  hematologic grade 4 are noted after 1 week at 280 mg daily, the Ibrutinib dose schedule will be increased to 420 mg daily.

If grade  $\geq$  3 non-hematologic toxicity and/or grade 4 hematologic toxicity are noted, a dose de-escalation to the prior dose level will be made. Resumption of treatment at this dose level may begin once Ibrutinib toxicity has improved to the grade 1 (or baseline) level.

If a  $\geq$  nonhematologic grade 3 or  $\geq$  hematologic grade 4 adverse event is noted in any one of the 5 subjects at the 140 mg dose level, a thorough review of this AE will be undertaken, and if deemed causative, treatment for that subject will be discontinued.

If a  $\geq$  nonhematologic grade 3 or  $\geq$  hematologic grade 4 adverse event is noted in  $>2$  of the 5 subjects at the 140 mg dose level, the study will be discontinued.

If a  $\geq$  nonhematologic grade 3 or  $\geq$  hematologic grade 4 adverse event is noted in a subject at the 280 mg dose level, the subject will then be dropped back to the prior dose level or treatment for that subject will be discontinued.

If a  $\geq$  nonhematologic grade 3 or  $\geq$  hematologic grade 4 adverse event is noted in a subject at the 420 mg dose level, the subject will then be dropped back to the prior dose level or treatment for that subject will be discontinued.

If therapy for 2 or more subjects at either the 280 mg or 420 mg dose level requires discontinuation, per the above parameters, no further escalation to those dose levels will be attempted for future patients.

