### 3.2 Primary Study Endpoints

1. Safety of combination Ibrutinib and Rituximab therapy for steroid refractory or dependent chronic GVHD, based on review of dose-limiting toxicities and results of the within-subject dose-escalation format.

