**Expansion cohort (additional 10 patients accrued) will be treated as follows:**

Ibrutinib 420 mg po once daily with

Rituximab 375 mg/m^2 IV weekly x4

If, based on above toxicity criteria, the Ibrutinib 420 mg daily dose schedule has been discontinued, then 280 mg po once daily will be the expansion cohort dose schedule

If, based on above toxicity criteria, the Ibrutinib 280 mg daily dose schedule has been discontinued, then 140 mg po once daily will be the expansion cohort dose schedule

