### Initial cohort (first 5 patients accrued) will be treated as follows:

Ibrutinib 140 mg po once daily with

Rituximab 375 mg/m^2 IV weekly x4 (with pre-medications and infusion procedure as per standard protocol)

Rituximab Pre-medications: Acetaminophen 650 mg po; Diphenhydramine 25 mg po/IV; Dexamethasone 20 mg IV

If no adverse events  $\geq$  nonhematologic grade 3 or  $\geq$  hematologic grade 4 are noted after 1 week at 140 mg daily, the Ibrutinib dose schedule will be increased to 280 mg daily

If no adverse events  $\geq$  nonhematologic grade 3 or  $\geq$  hematologic grade 4 are noted after 1 week at 280 mg daily, the Ibrutinib dose schedule will be increased to 420 mg daily.

If grade  $\geq$  3 non-hematologic toxicity and/or grade 4 hematologic toxicity are noted, a dose de-escalation to the prior dose level will be made. Resumption of treatment at this dose level may begin once Ibrutinib toxicity has improved to the grade 1 (or baseline) level.

If a  $\geq$  nonhematologic grade 3 or  $\geq$  hematologic grade 4 adverse event is noted in any one of the 5 subjects at the 140 mg dose level, a thorough review of this AE will be undertaken, and if deemed causative, treatment for that subject will be discontinued.

If a  $\geq$  nonhematologic grade 3 or  $\geq$  hematologic grade 4 adverse event is noted in  $>2$  of the 5 subjects at the 140 mg dose level, the study will be discontinued.

If a  $\geq$  nonhematologic grade 3 or  $\geq$  hematologic grade 4 adverse event is noted in a subject at the 280 mg dose level, the subject will then be dropped back to the prior dose level or treatment for that subject will be discontinued.

If a  $\geq$  nonhematologic grade 3 or  $\geq$  hematologic grade 4 adverse event is noted in a subject at the 420 mg dose level, the subject will then be dropped back to the prior dose level or treatment for that subject will be discontinued.

If therapy for 2 or more subjects at either the 280 mg or 420 mg dose level requires discontinuation, per the above parameters, no further escalation to those dose levels will be attempted for future patients.

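### The rule closing the 280 mg or 420 mg ibrutinib level counts discontinuations and does not say whether drop-backs count, so 420 mg could remain the expansion dose after repeated qualifying toxicity

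*Combined protocol and SAP*

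**What the plan says.** Section 5.1.1 treats the first 5 subjects at 140 mg, then 280 mg, then 420 mg, moving up after one week without a qualifying event (non-hematologic grade 3 or higher, or hematologic grade 4 or higher). Section 8.5 repeats the rules.

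- **General response to a qualifying toxicity:** "a dose de-escalation to the prior dose level will be made". No alternative is named in that sentence.
- **At 280 mg and at 420 mg:** "the subject will then be dropped back to the prior dose level or treatment for that subject will be discontinued". No criterion chooses between the two.
- **At 140 mg, single subject:** "a thorough review of this AE will be undertaken, and if deemed causative, treatment for that subject will be discontinued".
- **At 140 mg, whole study:** an event in more than 2 "of the 5 subjects at the 140 mg dose level, the study will be discontinued". This rule counts subjects with an event.
- **Closing an upper level:** "If therapy for 2 or more subjects at either the 280 mg or 420 mg dose level requires discontinuation", then "per the above parameters, no further escalation to those dose levels will be attempted for future patients".
- **Expansion cohort (10 subjects):** 420 mg by default. The step down to 280 mg applies under this condition: "If, based on above toxicity criteria, the Ibrutinib 420 mg daily dose schedule has been discontinued". A parallel sentence leads from 280 mg to 140 mg.

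Section 3.2 makes safety the primary endpoint, "based on review of dose-limiting toxicities and results of the within-subject dose-escalation format".

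**The concern.** The subject-level sentences set drop-back and discontinuation against each other as two different outcomes. The closure sentence then uses only the second term and points back to those parameters. Read in sequence, a subject who is dropped back has not been discontinued and does not count. The study-stopping rule at 140 mg has no such gap, because it counts events, and the protocol does not explain the change of counting unit at the higher levels.

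The gap matters most for grade 3 non-hematologic events. They qualify under Section 5.1.1 but fall below the grade 4 threshold that Section 4.4.1 lists among possible reasons to end participation, so drop-back is their likely handling.

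At stake is the starting dose of 10 of the 15 subjects, who go straight to the selected level without the intermediate steps. Section 1.5 says escalation was chosen because the combination's tolerability data came from patients who were not transplant recipients. If the rule leaves out a main way of managing the toxicities the escalation is meant to detect, it can pass a level the cohort did not tolerate.

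**Working it through.** The plan gives no operating characteristic for the closure rule, so there is no figure of its own to reproduce.

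**Inputs**
- n = 5 subjects in the escalation cohort (Section 5.1.1). All 5 are assumed to reach 420 mg; n = 4 is shown as a variant.
- Threshold of 2 subjects (closure sentence), counted separately at each level (assumption).
- e = chance that a subject has a qualifying event at the level. Not in the documents; 10%, 20% and 40% are assumed.
- d = share of those events that lead to discontinuation. Not in the documents; 0.25, 0.50 and 0.75 are assumed.
- Subjects are independent.

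**Formulas.** For a per-subject probability p, P(X ≥ 2 | n, p) = 1 − (1−p)^n − n·p·(1−p)^(n−1).
- If every qualifying event counts, p = e.
- If only discontinuations count, p = e·d.
- Discontinuations under this rule are a subset of qualifying events. The chance of 2 or more events with the level still open is therefore the difference of the two.

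**Worked case, e = 20%, d = 0.50, n = 5**
- Events counted: 1 − 0.8^5 − 5(0.2)(0.8^4) = 1 − 0.328 − 0.410 = 0.263.
- Discontinuations counted, p = 0.10: 1 − 0.9^5 − 5(0.1)(0.9^4) = 1 − 0.590 − 0.328 = 0.081.
- Difference: 0.181 (from unrounded values).

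**Probability that the level closes, n = 5**

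| Rule | e = 10% | e = 20% | e = 40% |
|---|---|---|---|
| Events counted | 0.081 | 0.263 | 0.663 |
| Discontinuations, d = 0.75 | 0.048 | 0.165 | 0.472 |
| Discontinuations, d = 0.50 | 0.023 | 0.081 | 0.263 |
| Discontinuations, d = 0.25 | 0.006 | 0.023 | 0.081 |

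**Probability of 2 or more events with the level still open**

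| Case | e = 10% | e = 20% | e = 40% |
|---|---|---|---|
| n = 5, d = 0.75 | 0.033 | 0.098 | 0.191 |
| n = 5, d = 0.50 | 0.059 | 0.181 | 0.400 |
| n = 5, d = 0.25 | 0.076 | 0.240 | 0.582 |
| n = 4, d = 0.50 | 0.038 | 0.129 | 0.344 |

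**Limits.** If every event is managed by drop-back (d = 0), the discontinuation count is always 0 and the level never closes. If every event leads to discontinuation (d = 1), the two rules coincide. On the reading that drop-back ends therapy at the level, the first row of the closure table applies whatever d is.

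**The case against.** The strongest reply is that the closure sentence concerns therapy at a dose level, and that a subject dropped back from 420 mg has stopped therapy at 420 mg. The expansion-cohort text supports this: it speaks of a dose schedule, not a subject, being discontinued. On that reading two drop-backs close the level and there is no gap. This stands as a genuine alternative. It does not remove the problem, because two careful readers could assign different doses to 10 patients from the same data.

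A reader might infer that the rule can never close 420 mg. The documents do not support that. It needs every event to be managed by drop-back, whereas the 280 mg and 420 mg sentences allow discontinuation. Section 4.4.1 lists inability to tolerate the dose as a reason to end participation. The duration-of-therapy text ends ibrutinib for significant side effects, though it also allows for an adjusted dose.

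A reader might also infer that toxicity in all 5 subjects is likely, or that 420 mg is unsafe. Section 1.5 cites phase 1b/2 data supporting ibrutinib 420 mg in post-transplant chronic GVHD, which makes high event rates less plausible, though it does not address the combination in that setting.

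Safeguards exist. The Study Summary says expansion dosing will be informed by the escalation results, Section 4.4.1 lets a protocol physician stop the study, and Section 10.2 gives the monitoring committee power to suspend it. None sets a threshold for drop-backs.

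Finally, the closure sentence could be read as pooling the two upper levels, which would close them more often than the figures above.

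**Conclusion.** The point holds as an ambiguity whose more natural reading leaves a safety gap. On that reading, 2 or more subjects (in the extreme, all 5) could have qualifying toxicity at 420 mg managed by drop-back, and the written rule would still send the expansion cohort to 420 mg. The protocol does not settle which reading applies.

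Across the assumed values with 5 subjects, the chance of 2 or more events with the level left open runs from 0.03 to 0.58. At d = 0.50 it is 0.06, 0.18 and 0.40 for event rates of 10%, 20% and 40%. It is small when events are rare. Event rate, discontinuation share, per-level counting and all subjects reaching the level are assumptions.

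The safety data themselves are not lost, since all adverse events are recorded. What is affected is the choice of expansion dose, and the wording should be corrected before that choice is made.

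**What to change.** In both Section 5.1.1 and Section 8.5, replace the closure sentence with:

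> *If 2 or more subjects have a non-hematologic grade ≥3 or hematologic grade ≥4 adverse event at the 280 mg or the 420 mg dose level, whether managed by drop-back or by discontinuation, that level and any level above it are closed for future patients.*

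This keeps the protocol's threshold of 2. Do not add a requirement that events be judged causative, or a cut-off after which events stop counting. The present rule for 280 mg and 420 mg has neither, so either addition would loosen it. The new sentence counts within each level; if the sponsor intends to pool the two levels, it should say so.

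The cost is one sentence in each of two sections and no additional patients. The downside is that a tolerable level is closed more often. With 5 subjects and half of events leading to discontinuation, closure is 0.08 rather than 0.02 at a 10% event rate, and 0.26 rather than 0.08 at 20%. Without a causality filter, some of those closures will be for events unrelated to ibrutinib.

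### Exactly two causative discontinuations at 140 mg leave the expansion dose at 420 mg, while two discontinuations at 280 or 420 mg lower it

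*Combined protocol and SAP*

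**What the plan says.** Section 5.1.1 of the combined protocol and SAP takes each of the first 5 subjects from 140 to 280 to 420 mg of ibrutinib, one week per step. A qualifying event is a non-hematologic adverse event of grade 3 or higher, or a hematologic one of grade 4 or higher. The rules that matter here are:

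- **140 mg, single subject:** "a thorough review of this AE will be undertaken, and if deemed causative, treatment for that subject will be discontinued".
- **140 mg, cohort:** if a qualifying event occurs in more than two "of the 5 subjects at the 140 mg dose level, the study will be discontinued". This rule counts events and sets no causality condition.
- **280 mg, single subject:** a qualifying event leads either to a drop-back or to discontinuation ("at the 280 mg dose level, the subject will then be dropped back to the prior dose level or treatment for that subject will be", where the sentence closes with discontinuation). The sentence for 420 mg has the same form.
- **Closing a level:** "If therapy for 2 or more subjects at either the 280 mg or 420 mg dose level requires discontinuation, per the above parameters", then "no further escalation to those dose levels will be attempted for future patients".
- **Expansion dose:** 420 mg by default; 280 mg if the 420 mg schedule has been discontinued; and if "the Ibrutinib 280 mg daily dose schedule has been discontinued, then 140 mg po once daily will be the expansion cohort dose schedule".

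Section 8.5 repeats these rules. Sections 4.4.1 and 7.2 say that subjects who withdraw for toxicity are not replaced. The Study Summary says only that the escalation results will inform expansion dosing.

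**The concern.** Discontinuations at 140 mg do not enter the count that closes 280 or 420 mg. A subject stopped at 140 mg also never reaches the higher levels, so that subject cannot be counted there later. At one particular count, the rules therefore let failure at the lowest dose lead to a higher expansion dose than the same number of failures at a higher dose.

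This matters because safety, judged from dose-limiting toxicities and the escalation results, is the primary endpoint (section 3.2). Section 1.5 explains that escalation is used because the existing combination data come from patients who were not transplant recipients. The rules fix the dose for 10 of the 15 subjects. If they can return 420 mg after 2 of 5 subjects (40%) were stopped at the starting dose, the dose decision does not follow from the trial's own toxicity data.

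**Working it through.** **Plan's own figure.** The documents give no operating characteristic for the toxicity rules, so there is none to reproduce. The only stated calculations are the efficacy powers in section 7.1. They reproduce (0.849 against the stated 85% for 6 of 15; 0.828 against 0.83 for 4 of 10) and play no part below.

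**Step 1: trace the rules.** Let k of the 5 subjects be discontinued at one level and none at the others. At 140 mg, all k events are judged causative and no other subject has a qualifying event. The 280 and 420 mg counts are read level by level, as the separate fallbacks in the expansion text of 5.1.1 imply. The expansion dose is then:

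| k | all at 140 mg | all at 280 mg | all at 420 mg |
|---|---|---|---|
| 0 or 1 | 420 mg | 420 mg | 420 mg |
| 2 | 420 mg | 140 mg | 280 mg |
| 3 or more | study stopped | 140 mg | 280 mg |

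Only the row k = 2 is out of order.

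**Step 2: what is left to judge the higher doses.** With two subjects lost at 140 mg and no replacement, at most 5 − 2 = 3 can inform 280 and 420 mg, while the closing threshold stays at 2.

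- Two discontinued at 140 mg plus one at 280 mg or one at 420 mg: 3 of 5 stopped, expansion still at 420 mg. This holds whether the upper two levels are counted separately or together.
- Two at 140 mg, one at 280 mg and one at 420 mg: 4 of 5 stopped, expansion still at 420 mg. This holds only on the level-by-level count.

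**Step 3: how often k = 2 could arise.** The documents give no event rate at 140 mg, so p is an assumption. Let X be the number of the 5 subjects with a qualifying event at 140 mg, independent with common probability p:

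P(X = 2) = 10 p² (1 − p)³

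For p = 0.2 this is 10 × 0.04 × 0.512 = 0.2048.

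| p (assumed) | P(X ≤ 1): levels do not differ | P(X = 2): no cohort rule acts | P(X ≥ 3): study stops |
|---|---|---|---|
| 0.1 | 0.9185 | 0.0729 | 0.0086 |
| 0.2 | 0.7373 | 0.2048 | 0.0579 |
| 0.3 | 0.5282 | 0.3087 | 0.1631 |
| 0.4 | 0.3370 | 0.3456 | 0.3174 |

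**Step 4: causality.** A third qualifying event of any cause stops the study. The problem case therefore needs exactly two events, both judged causative. If each event is judged causative independently with probability c, the chance is P(X = 2) × c², which is at most P(X = 2). The third column is thus an upper bound, reached at c = 1.

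**Step 5: the same toxicity placed at another level.** Suppose events occur at one level only and every event ends in a causative discontinuation.

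- Events at 140 mg only: the 420 mg expansion opens with probability P(X ≤ 2).
- Events at 280 mg only, or at 420 mg only: it opens with probability P(X ≤ 1).

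The difference is exactly P(X = 2). At p = 0.2 it is 0.9421 − 0.7373 = 0.2048; at p = 0.4 it is 0.6826 − 0.3370 = 0.3456.

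**The case against.** The case for the plan has several parts, and most of them limit the point.

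- **The 140 mg rule is the strictest at three or more.** It stops the whole study and needs no causality finding. A reader might infer that toxicity at 140 mg always restricts the expansion less than toxicity higher up. The table in the working shows otherwise: three or more events stop the study, and zero or one makes no difference.
- **The rules do not contradict each other.** All of them can be followed at once. The fault is that the dose outcomes are out of order at k = 2.
- **Events at 280 or 420 mg need not end in discontinuation.** Section 5.1.1 also allows a drop-back, which read literally does not count towards closing a level. Two subjects dropped back from 280 mg would leave 420 mg open too. The contrast therefore holds only for discontinued subjects. This is a further gap and does not close the one described here.
- **The event rate at 140 mg may be low.** The step lasts one week, and section 1.4 describes toxicity of the combination in CLL as mostly mild to moderate. At p = 0.1 the bound is 0.07. But those patients were not transplant recipients, which is the protocol's own reason for escalating.
- **There is room for judgement.** The Study Summary refers to the escalation results, a 140 mg event must be reviewed, any protocol physician may stop the study (4.4.1), and the DSMAC may suspend it (10.2). A reader might infer from the rules that ten subjects would go to 420 mg with no one able to intervene, and these provisions do not support that. Equally, none of them says how 140 mg discontinuations enter the dose choice, and the specific expansion rule has a fixed default.

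**Conclusion.** The dose-decision rule is wrong as written, at one count. With exactly two causative discontinuations at 140 mg among the first 5 subjects, no cohort-level rule acts and the expansion stays at 420 mg. Two discontinuations at 280 mg give 140 mg, and two at 420 mg give 280 mg. At most three subjects would then have informed the higher doses.

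For p of 0.1, 0.2, 0.3 or 0.4, the chance of reaching this point is at most 0.07, 0.20, 0.31 or 0.35. This rests on an assumed, common and independent event probability, and on both events being judged causative. The larger probability that the study is not stopped at 140 mg (0.94 at p = 0.2) should not be read as the size of the problem, because it includes zero and one event, where nothing is out of order.

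The dose outcomes rest on the level-by-level reading of the closing rule. If discontinuations at either upper level closed both, two at 420 mg would lead to 140 mg instead, and the k = 2 inversion would remain.

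**What to change.** Amend sections 5.1.1 and 8.5 together. Reconcile the 140 mg rule, the closing rule for 280 and 420 mg and the expansion-dose rule, so that the documents say consistently whether and how discontinuations at 140 mg bear on the expansion dose. The same amendment can state whether the 280 and 420 mg counts are separate and whether drop-backs count. The counting rule, the threshold and the resulting dose are for the investigator and the DSMAC to set, and none is proposed here.

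The cost is a short clarifying text in two sections, with no added subjects or procedures. The downside is small: depending on what is decided, the expansion dose could be restricted somewhat more often.
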